5.7.1.7. Immunogenicity against the vector

For immunogenicity against the Ad26 vector backbone (Adenovirus neutralization by neutralization assay), the following statistics will be calculated: geometric mean and corresponding 95% CI of the actual values, and number and percentage of participants with a positive sample.

If only one time point is available, then actual values at that single time point will be shown as a dot plot. If multiple time points are available, then GMT plots over time, combining the regimens in one graph (without individual participant dots) will also be generated. In addition, participant profiles will then also be created.

5.7.1.8. Antibodies binding to the SARS-CoV-2 nucleocapsid (N) protein

For antibodies binding to the SARS-CoV-2 nucleocapsid (N) protein, the number and percentage of participants with a positive sample at Day 1, Day 29, Day 71, and Day 181 will be tabulated. A positive or negative result will be obtained from the assay (qualitative assay).

In contrast to the other immunogenicity analyses, this analysis will be performed only on the FAS.

The definition of the PPI analysis set incorporates the N-serology sample positivity assessment: immunogenicity samples obtained after a positive N-serology sample will be excluded from the PPI analysis.

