
To explore the rVE of different dose levels of Ad26.COV2.S heterologous booster vaccination in the prevention of SARS-CoV-2 infection (severe/critical, moderate, moderate to severe/critical, symptomatic, and asymptomatic infections, that are serologically and/or molecularly confirmed) as follows:
 
 – 5×10^{10}vp versus 1×10^{10}vp dose level – 2.5×10^{10}vp versus 1×10^{10}vp dose level 	
post vaccination in COV2008, if sufficient data are available.
 
 • Asymptomatic cases of COVID-19, as determined by seropositivity for the SARS-CoV-2 N protein. • SARS-CoV-2 infections as detected by molecular testing (RT-PCR or equivalent). • COVID-19 cases meeting the US FDA Harmonized COVID-19 case definition, with onset at least 14 days post vaccination in COV2008. • COVID-19 cases meeting the criteria for “moderate, moderate to severe/critical and severe/critically ill” COVID-19, with onset at least 14 days post vaccination in COV2008, if sufficient data are available.

If feasible, to investigate the effect of post booster cellular responses, mRNA profiles, neutralizing responses and/or other functional antibody responses on the probability of experiencing a COV ID-19 event, moderate and moderate to severe/critically ill COVID-19 disease, or asymptomatic SARS-CoV-2 infection.
	
 • Serological response to vaccination and antibody titers as measured by virus neutralization assay (VNA) titers against the reference strain and/or SARS-CoV-2 variants, by ELISA/MSD and/or other functional antibody assays, 14 days, 6 months and 1 year after homologous or heterologous booster vaccination with Ad26.COV2.S, if sufficient data are available. • Cellular response to vaccination as measured by flow cytometry, ELISPOT and/or transcriptomics, 14 days, 6 months and 1 year after homologous or heterologous booster vaccination with Ad26.COV2.S, if sufficient data are available. • COVID-19 cases meeting the US FDA Harmonized COVID-19 case definition, with onset at least 14 days post booster vaccination in study COV2008, if sufficient data are available. • COVID-19 cases meeting the criteria for “moderate and moderate to severe/critically ill” COVID-19, with onset

Exploratory Objectives	Endpoints

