5.2.5.2. Classification

Asymptomatic infections or undetected cases will be classified using a similar algorithmic approach. Cases will then be reviewed and classified by the CSAC.

Relevant definitions for programmed algorithm

Identification of potential asymptomatic SARS-CoV-2 infections via PCR: Cases with a positive PCR will be reviewed for the presence of signs and/or symptoms of COVID-19 employing the definitions of onset and resolution of section 5.2.2. In the absence of signs and/or symptoms, the case will be classified per algorithm as asymptomatic.

Identification of potential asymptomatic or undetected SARS-CoV-2 infections through seroconversion:

- **SARS-CoV-2 seroconversion by N-serology with onset Day >14** is based on the available data from Day 71, Month 6. If positive at any timepoint while the subject was seronegative at baseline (and at Day 15 for the PPE analysis after day 14), a subject is considered to have seroconverted. If Day 14 is missing or not available, the subject is considered to be negative on that day.
- **SARS-CoV-2 seroconversion by N-serology from Day 1 to Day 14**, is based on the available data on day 14. If positive at day 14 while the subject was seronegative at baseline or missing, a subject is considered to have seroconverted between day 1 and day 14.
- **A seroconverted participant** is a subject with serological conversion without an earlier SARS-CoV-2 positive RT-PCR or molecular test result from any available respiratory tract sample.

Upon algorithmic classification, cases will be evaluated as being an "Asymptomatic SARS-CoV-2 infection" by the Clinical Severity Adjudication Committee as follows:

- Asymptomatic SARS-CoV-2 infections or seroconverted participants as assigned via the programmed algorithm will be reviewed for the presence of possible COVID-19 signs and symptoms from baseline up to 7 days prior to the first positive PCR or up to the day of the first positive serology test.
- If no presence of signs/symptoms, the algorithm will be accepted and no further review by the CSAC and the case classified as Asymptomatic SARS-CoV-2 infection.
- If at least one sign or symptom is present, those cases will be sent to the CSAC for review for a possible undetected symptomatic COVID-19 illness.
 - If reviewed by the CSAC as asymptomatic SARS-CoV-2 infections, cases will be classified as asymptomatic infection.

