4. POPULATIONS (ANALYSIS SETS) FOR ANALYSIS

For vaccine studies, study intervention assignment will follow the *as treated principle* i.e., all analyses will be presented by the vaccine actually received.

Population	Description
All screened participants (ALL)	The “all screened participants” set includes all participants who were screened, regardless of whether they were enrolled and/or randomized.
All randomized participants (ALL RANDOMIZED)	The “all randomized participants” set includes all participants who were randomized to one of the treatment groups.
Full Analyses Set (FAS)	The full analysis set includes all participants with documented study vaccine (Ad26.COV2.S) administration.
Per Protocol Immunogenicity Set (PPI)	The per protocol immunogenicity analysis set includes all vaccinated participants for whom post-baseline immunogenicity data are available and excludes participants with major protocol deviations expected to impact immunogenicity outcomes. In addition, samples obtained after natural SARS-CoV-2 infection will be excluded from this analysis set.
Non-Inferiority Analysis Set (NI)	The non-inferiority analysis set includes all PPI participants who are SARS-CoV-2 seronegative at baseline.

Pfizer BNT162b2 external samples	The Pfizer BNT162b2 external samples analysis set includes individuals, selected from biobanks or clinical studies, who received 2 doses of Pfizer BNT162b2 vaccine as primary vaccination and for whom blood samples are available between 2 weeks and 2 months post primary vaccination series with Pfizer BNT162b2 vaccine.
----------------------------------	--

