5.7.1. Immunogenicity

5.7.1.1. Immunogenicity Analysis

The analysis of immunogenicity will use the PPI and NI analyses sets. Selected immunogenicity analyses may also be done on the FAS. Within each Cohort (Cohort 1 (Ad26.COV2.S primary vaccination); Cohort 2 (BNT162b2 primary vaccination)), data will be analyzed by vaccine group, and by vaccine group and participant seropositivity status at screening. Data will be presented by scheduled time point. Selected results will be presented in the same output with both cohorts.

For the PPI analysis, samples taken outside of the allowed window will be excluded from the tables and graphs (but will be included in the listings and clearly marked as results not included in the PPI analyses). For the FAS analysis, samples taken outside of the window will be included.

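### The main SAP's two PPI exclusion rules disagree on the titre from the first N-positive visit: section 4 drops it, but section 5.7.1.8 read literally keeps it

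*SAP*

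**What the plan says.** Main SAP section 4 defines the PPI set and adds that "samples obtained after natural SARS-CoV-2 infection will be excluded from this analysis set". It does not limit how the infection was found.

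Main SAP section 5.7.1.8 links that definition to N-serology. It says "The definition of the PPI analysis set incorporates the N-serology sample positivity assessment" and then gives the rule: "immunogenicity samples obtained after a positive N-serology sample will be excluded from the PPI analysis". The same section lists the N time points to be reported: "participants with a positive sample at Day 1, Day 29, Day 71, and Day 181 will be tabulated".

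Main SAP section 5.7.1.1 fixes where the rule acts: "The analysis of immunogenicity will use the PPI and NI analyses sets", with results shown by scheduled time point. Section 5.4 makes neutralising titres 14 and 28 days after the booster secondary endpoints. Supplemental SAP section 1.1 adds exploratory antibody titres "14 days, 6 months and 1 year after homologous or heterologous booster vaccination with Ad26.COV2.S, if sufficient data are available".

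On late infections, supplemental SAP section 5.2.5.2 states that N-seroconversion with onset after Day 14 "is based on the available data from Day 71, Month 6". Its section 5.3.2 presumes that Omicron dominates the observation period.

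**The concern.** N-serology dates an infection only to the interval before the first positive draw. A rule that starts after the positive sample therefore begins one visit too late for an infection found only by N-serology. The titre measured at that visit has already been raised by the infection, yet section 5.7.1.8 does not remove it. Section 4 would. A programmer is likely to follow the explicit rule.

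The retained titres would make late PPI GMTs and fold rises look more durable than the booster made them. If one dose level or cohort has more infections, which is what the supplemental SAP sets out to compare, its late titres are inflated more. That could mask or reverse a real difference between arms.

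**Working it through.** The plan gives no figure on this point, so there is none to reproduce. The check has three parts: the two rules applied to one participant, the spacing of the N days, and an illustration of size.

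**1. The two rules applied to one case.** Take a participant who is N-negative at Day 71, is infected at, say, Day 120 with no positive PCR, and is first N-positive at Day 181. Assume that the N sample and the titre sample belong to the same visit; the SAP does not say so.

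| Sample | Main SAP section 4 (after infection) | Main SAP section 5.7.1.8 (after a positive N sample) |
|---|---|---|
| Day 29 titre | kept | kept |
| Day 181 titre | excluded | kept |
| 1-year titre | excluded | excluded |

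The sections disagree only on the first N-positive visit. The plan expects such participants: supplemental SAP section 5.2.5.2 defines a seroconverted participant as one with no earlier positive molecular test.

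**2. Where the gap is widest.** From the listed days 1, 29, 71 and 181:

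- 29 − 1 = 28 days
- 71 − 29 = 42 days
- 181 − 71 = 110 days

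The last interval covers 110 / (181 − 1) = 110 / 180 = 61% of the time to Month 6. Infections in that interval that only N-serology finds can first show at Day 181, so the Month 6 titre carries most of the exposure. The Day 29 titre, a secondary endpoint, is open to the same fault over a 28-day interval, where fewer infections are expected.

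**3. Illustrative size.** Let p be the share of retained samples at a time point that follow infection, and F the fold rise in titre due to infection. Suppose that without infection these participants would have had the same mean log titre as the others. The mean log titre then shifts by p × log F, and the GMT is multiplied by F^p. Fold rises from a baseline before infection shift by the same factor. Neither p nor F is in the documents; both are assumptions.

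| p | F | F^p |
|---|---|---|
| 5% | 4 | 1.07 |
| 10% | 4 | 1.15 |
| 20% | 10 | 1.58 |
| 30% | 10 | 2.00 |

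For two arms with p = 10% and p = 25% and F = 10, a true GMT ratio of 1 would be estimated as 10^(0.25 − 0.10) = 10^0.15 = 1.41 in favour of the arm with more infections.

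**The case against.** The strongest reply is that section 4 is the governing definition. It already excludes anything taken after natural infection, and section 5.7.1.8 only says that N-serology is incorporated in it. On that view the N rule is one input, PCR-confirmed infections are covered in principle, and the wording gap is a matter of clarification. Much of this stands. What remains is that the only rule explicit enough to program gives the opposite result to section 4 at the first N-positive visit.

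A reader might go further and infer that the PPI rule removes only samples after an N-positive result, that N-testing stops at Day 181, and that infection-boosted titres therefore stay throughout the 6-month and 1-year results. The documents do not support this:

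- Section 4 reaches known infections however they were detected. At most, the SAP does not spell out that a PCR date triggers exclusion.
- The days in section 5.7.1.8 are those to be tabulated and are not a sampling schedule. Main SAP section 5.8.2 and supplemental SAP section 5.2.5.2 both refer to N-serology at about Day 14 or 15, which is not on that list. The visit schedule is in the protocol, which is not shown.
- A participant N-positive by Day 71 loses the 6-month and 1-year samples even under section 5.7.1.8 alone.
- No Day 71 titre endpoint is shown.
- Correlates of risk are deferred to a separate document (supplemental SAP section 5.1.4), so an effect on that analysis is not established.

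It is also fair that p and F are not trial data. Since p should count only infections not otherwise known, the upper rows of the table may be unrealistic.

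**Conclusion.** The point holds in a limited form. Main SAP sections 4 and 5.7.1.8 conflict on the titre from the first N-positive visit, and the rule in 5.7.1.8 keeps a post-infection value that section 4 means to remove. This rests on the N and titre samples sharing a visit, which is a reasonable reading but is not stated.

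The effect is greatest at Day 181 and smaller at Day 29. Its size cannot be taken from the documents; the range of about 1.07 to 2.0 in GMT depends wholly on the assumed p and F. The 6-month and 1-year titres are exploratory and conditional on sufficient data. The primary non-inferiority comparison at Day 15, in baseline-seronegative participants, is not affected by the late time points.

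For the 1-year titre, only a conditional statement is possible: if no N result exists after Day 181, infections after that day without a positive molecular test cannot be identified.

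**What to change.** Reword the rule in main SAP section 5.7.1.8 to match section 4: samples obtained on or after the date of the first positive N-serology sample, or on or after the date of a positive SARS-CoV-2 molecular test, whichever is earlier, are excluded from the PPI analysis.

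If the protocol schedule provides no N-serology after Day 181, report the 1-year PPI titres with the caveat that, for infections after Day 181, only those detected by a molecular test are excluded.

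The cost is one changed sentence and one changed date comparison in the derivation, with the molecular test date added. Somewhat fewer late samples will remain in the PPI set.

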5.7.2. Definition of Subgroups

Selected safety and immunogenicity analyses will be conducted by the following subgroup.

Subgroup	Definition
Age Group (years)	
 • ≥ 18 to < 60 • ≥ 60

5.8. Interim, and Planned Analyses

This SAP applies to all planned analyses of this study per CTP section 9.5 (primary analysis and final Analysis) in addition to the immunogenicity interim analysis that may be conducted on Cohort 1 data.

5.8.1. Interim Analysis

When at least 330 participants (see CTP Section **Error! Reference source not found.**) from Groups 1 to 3 in Cohort 1 have been enrolled and completed the Day 15 visit, it is estimated that immunogenicity data can be obtained from at least 110 participants in Group 1 to potentially

conduct an interim analysis. The planned primary non-inferiority testing of Cohort 1 – Group 1 may be performed on the available data from the Cohort 1 – Group 1 participants.

Scope of the Interim Analysis:

The interim analysis will consist of a statistical immunogenicity analysis of Cohort 1 – Group 1 participants only. Hypotheses 1a and 1b will be tested, in the hierarchical manner as outlined in **Error! Reference source not found.** (see CTP): Hypothesis 1b will only be tested if all success criteria of Hypothesis 1a are met. The other hypotheses (1c, 1d, 2a, 2b and 2c) will only be tested at the primary analysis.

In addition, limited safety/reactogenicity statistical outputs will be generated in a blinded manner, for all available participants (Cohort 1 and Cohort 2, all groups). The same outputs will be generated in an unblinded manner by the independent Statistical Support Group and will be shared only with the IDMC. The unblinded outputs may also be used to respond to questions or requests from Health Authorities. In this case, appropriate channels of communication will be used to keep the Sponsor blinded.

Alpha Spending:

An O'Brien-Fleming adjustment will be used whereby the type I error for the NI test at the interim analysis will be 0.0003 (one-sided). This alpha is calculated based on an estimated interim analysis sample size of 110 Cohort 1 – Group 1 participants (~33% of the total sample size). If immunogenicity data is available for more than 110 Cohort 1 – Group 1 participants at the time of the interim analysis, then the nominal alpha level of the interim analysis will be kept at 0.0003, but the alpha level at the primary analysis will be recalculated. The recalculation will be based on the O'Brien-Fleming adjustment and will take into consideration the alpha spent at the time of the interim analysis and the actual information fraction that was available at the time.

Procedures to maintain the study blind:

This interim analysis will be conducted by an independent Statistical Support Group. Only group-level unblinded immunogenicity statistical outputs and blinded safety/reactogenicity statistical outputs will be available to the Sponsor.

In order to keep the blind at the laboratory, all available Cohort 1 immunogenicity samples, from all groups, will be shipped and analyzed, if operationally feasible. In case a selection of samples is needed for operational reasons, the selection will be made in advance by the independent Statistical Support Group and this selection will include, next to the Cohort 1 – Group 1 samples, also at least 20 samples of Cohort 1 – Group 2 and at least 20 samples of Cohort 1 – Group 3.

5.8.2. Planned Analysis

The primary and final analyses of Cohort 1 may be performed before the analyses of Cohort 2.

The primary analysis of safety and immunogenicity in Cohort 1 or Cohort 2 will be performed when all evaluable participants in the respective cohort have completed the visit that takes place 28 days after study vaccination or discontinued earlier. The analysis will include immunogenicity data (VNA, S-ELISA, N-serology) for all evaluable participants through Day 15, and all available safety data. The sponsor will be unblinded for the respective cohort at the time of this primary analysis, but the blind will be maintained at the participant and study site level up to study end.

The final analysis in Cohort 1 or Cohort 2 will be performed when all included participants in the respective cohort have completed their last visit or discontinued earlier.

5.9. Independent Data Monitoring Committee (IDMC)

An Independent Data Monitoring Committee (IDMC) has been commissioned to review the safety data of this trial alongside the other COVID-19 trials. Please refer to the associated IDMC Charter.

6. SUPPORTING DOCUMENTATION

6.1. Appendix 1 List of Abbreviations

Ad26	adenovirus type 26
AE	adverse event
AESI	adverse event of special interest
ALT/SGPT	alanine aminotransferase
ANCOVA	analysis of covariance
AST/SGOT	aspartate aminotransferase
ATC	anatomic and therapeutic class
AUC	area under the curve
BMI	body mass index
BNT162b2	Pfizer mRNA- based SARS-CoV-2 vaccine
BSA	body surface area
CI	confidence interval
COVID-19	coronavirus disease-2019
CRF	case report form
CSR	Clinical Study Report
CTCAE	Common Terminology Criteria for Adverse Events
CV	coefficient of variation
DMC	Data Monitoring Committee
DPS	Data Presentation Specifications
ECG	electrocardiogram
eCRF	electronic case report form
F (%)	absolute SC bioavailability
FAS	full analysis set
FDA	Food and Drug Administration
GMR	geometric mean ratio
GMC	geometric mean concentration
GMT	geometric mean titer
ICH	International Conference on Harmonisation
IQ	interquartile
IVRS	interactive voice response system
IWRS	interactive web response system
LLOQ	lower limit of quantification
LOCF	last observation carried forward
MedDRA	Medical Dictionary for Regulatory Activities
MRD	minimum required dilution
NAb	neutralizing antibodies
PD	pharmacodynamic(s)
PI	principal investigator
PK	pharmacokinetic(s)
PP	per protocol
SAE	serious adverse event
SAP	Statistical Analysis Plan
SD	standard deviation
SMQs	standardised MedDRA queries
TEAE	treatment-emergent adverse event
Tmax	time to maximum concentration
US NCI	United States National Cancer Institute
V	volume distribution
vp	virus particle
Vz	volume of distribution based on terminal phase
Vz/F	apparent volume of distribution based on terminal phase after extravascular administration
WHO	World Health Organization
WHO-DD	World Health Organization Drug Dictionary

6.2. Appendix 2 Changes to Protocol-Planned Analyses

6.3. Appendix 3 Demographics and Baseline Characteristics

The following demographic and baseline characteristics will be summarized.

[Table 2](#) presents a list of the demographic and baseline variables that will be summarized by vaccine regimen and overall for the FAS.

Table 2: Demographic Variables

Continuous Variables:	Summary Type
Age (years)	Descriptive statistics (N, mean, standard deviation [SD], median and range [minimum and maximum]).
Weight (kg)	
Height (cm)	
Body Mass Index (BMI) (kg/m ²)	
Categorical Variables	
Sex (male, female, undifferentiated)	
Race ^a (American Indian or Alaska Native, Asian, Black or African American, Native Hawaiian or other Pacific Islander, White, Multiple)	
Ethnicity (Hispanic or Latino, not Hispanic or Latino)	
Study center	
SARS-CoV-2 Seropositivity status at screening	
Age (years):	
• ≥18 to <60	
• ≥60	

^aIf multiple race categories are indicated, the Race is recorded as 'Multiple'

6.4. Appendix 4 Protocol Deviations

In general, the following list of major protocol deviations may have the potential to impact participants' rights, safety or well-being, or the integrity and/or result of the clinical study. Participants with major protocol deviations will be identified prior to database lock and the participants with major protocol deviations will be summarized by category.

- Developed withdrawal criteria but not withdrawn
- Entered but did not satisfy criteria
- Received a disallowed concomitant treatment
- Received wrong treatment or incorrect dose
- Other

Major protocol deviations which have a potential impact on immunogenicity will be flagged in the listings.

